Section 9.2.7.4.5 Case ascertainment for malaria: Definition for cerebral malaria cases added together with details of GSK safety physician review and review by two selected experts.

Section 9.2.7.6 Capacity building: Details of training packages for site staff.

Section 9.3.3.1 Recorded in EPI-MAL-002 and EPI-MAL-003: Reworded.

Section 9.3.3.2 Recorded in EPI-MAL-005: Reworded.

Section 9.4.1 Health Demographic Surveillance System: Small updates.

Section 9.4.2 Active surveillance and enhanced hospitalisation surveillance of study EPI-MAL-002: New first paragraph plus other updates.

CONFIDENTIAL115055 (EPI-MALARIA-002 VS AME)
Protocol Amendment 7 Final

Section 9.4.3 Malaria Transmission Intensity Study EPI-MAL-005: Details of enrolling subjects in EPI-MAL-002 and EPI-MAL-005 studies plus other small updates.

Section 9.5 Study size: Updated text.

Section 9.7 Data analysis: Text on descriptive analysis of safety endpoints.

Section 9.7.4.1 Sequence of analyses: Details of interim analysis added.

Section 9.7.5.1 Analysis population: Small update.

Section 9.7.5.2.1 Incidence of AESI, and other AE leading to hospitalisation or death: Small updates.

Section 9.7.5.2.2 Incidence rate of aetiology-confirmed meningitis: Small updates.

Section 9.7.6.2 Statistical approach: Updates to text.

Section 9.7.7 Analysis for other secondary objectives: Small updates.

Section 9.7.7.1 Analysis population: New text on Main and Complementary analyses.

Section 9.7.7.2 Statistical approach: Updates including updates to Table 8.

Section 9.7.8.1 Handling of missing data: Details of a sensitivity analysis added.

Section 9.8.2 Archiving of data at study sites: Small update.

Section 9.9 Limitations of the research methods: Updates included length of follow-up, malaria transmission intensity for sites and the interim analysis.

Section 10.1 Regulatory and ethical considerations, including the informed consent process: Small update.

Section 12 Plans for disseminating and communicating study results: Details on the interim report added.

Section 13 References: Added both European Medicines Agency references plus, Rubin, Sterne, The RTS,S Clinical Trials Partnership, WHO - Global malaria programme, WHO - Management of severe malaria, and WHO - Background brief: malaria vaccine RTS,S/AS01 references, removed the GlaxoSmithKline study report reference, and made updates to other references e.g. updating date last accessed.

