- Shock: compensated shock is defined as capillary refill $\geq 3 \text{ s}$ or temperature gradient on leg (mid to proximal limb), but no hypotension. Decompensated shock is defined as systolic blood pressure $< 70 \text{ mm Hg}$ in children, with evidence of impaired perfusion (cool peripheries or prolonged capillary refill);
- Hyperparasitaemia: *P. falciparum* parasitaemia $> 10\%$ (i.e. percentage of infected red blood cells $> 10\%$; corresponding to $> 500,000/\mu\text{L}$).
- Severe vivax malaria is defined as for severe falciparum malaria but with no parasite density thresholds [[WHO, 2015\(b\)](#)].
- Cerebral malaria [adapted from [WHO, 2015\(b\)](#)]:
Severe *P. falciparum* malaria with impaired consciousness (Glasgow coma score < 11 in children ≥ 2 years of age or Blantyre coma score < 3 in children < 2 years of age);

AND

If malaria with seizure: coma persisting for $> 30 \text{ min}$ after the seizure.

Other treatable causes of coma should be excluded before diagnosing cerebral malaria (e.g. hypoglycaemia, bacterial meningitis).

Note: Suspected malaria cases routinely tested using RDT will have a blood smear for reading by microscopy in parallel, in order to measure sensitivity and specificity. This will be done for all suspected cases presenting at primary health care facilities one day per month during the first year of the study.

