Follow-up children up to study conclusion, by a check-up at the hospital 1 month, 6 months and 1 year after hospital discharge	•	
Only for subjects with suspected malaria		
For suspected malaria, record malaria microscopy and/or RDT or other result	•	
Study conclusion		•

Hospitalisation visits: subjects aged < 5 years, to include subjects referred in between active surveillance visits.

- is used to indicate a study procedure that requires documentation in the individual eCRF
- is used to indicate a study procedure that does not require documentation in the eCRF

1. See [Annex 6](#)
2. All immunisations will be recorded
3. See Study Procedures Manual (SPM)
4. See [Annex 5](#)
5. See Section [9.2.7.3.1](#)
6. For subjects not enrolled previously
7. Because of a possible overlap of studies EPI-MAL-002 and EPI-MAL-003, study conclusion of EPI-MAL-002 for children enrolled in enhanced hospitalisation surveillance will be done at start of study EPI-MAL-003 (as the RTS,S/AS01E vaccine becomes available in the sites that are exposed clusters).

(Amended 5 May 2020)

CONFIDENTIAL115055 (EPI-MALARIA-002 VS AME)
Protocol Amendment 7 Final**9.2.7.3. Biological sample handling and analysis****9.2.7.3.1. *Biological samples***

All enrolled subjects admitted to the hospital are expected to have routine laboratory tests performed according to good medical practice and routine practice (see Section 9.2.7.5), including, but not limited, to:

- All hospitalised children: haemoglobin concentration or full blood count
- Malaria suspects: Access to diagnosis of malaria using RDT and/or microscopy according to routine practice will be ensured for all children clinically suspected of malaria during active surveillance and at all the health care facilities.
- Meningitis suspects: CSF examination (and blood culture if feasible) according to routine practice (first line testing).
- Neurological diseases such as seizures, encephalitis, Acute Disseminated Encephalo-Myelitis (ADEM), Guillain Barre syndrome suspected: require neurological investigations (e.g. magnetic resonance imaging if available), eventually CSF analysis and other laboratory testing according to routine practice.
- Some AESI (such as diabetes mellitus, renal failure, hepatic failure, severe thrombocytopenia with bleeding) require laboratory testing for case management.

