9.2.7.4.2. Case ascertainment for AESI

In the event of diagnosis of a disease specified as an AESI during routine care, case ascertainment will result in a diagnosis reaching the highest level of case definition at the hospital possible (see [Table 3](#) and [Annex 5](#)). As part of good medical practice, study clinical staff will ensure appropriate diagnostic testing and adequate care to enrolled, hospitalised children diagnosed with a disease specified as an AESI as per National guidance (see Section 9.2.7.5). As diagnosis of these events may be challenging, the investigators and site physicians will be supported by specialized health care professionals, if required (see Section 9.2.7.6).

In addition, a panel of experts in the different fields will perform ascertainment of AESI with an uncertain diagnosis and outcome after review by the GSK safety physician. These cases will be flagged in the eCRF during the manual cleaning by the GSK safety physician, for external expert review. Two selected experts will independently review the cases. They will be provided with all available medical information (e.g. medical and family history, physical examination, clinical presentation/picture, laboratory results, concomitant medication/vaccination and any other relevant information identified in patient medical records) and classify the cases according to the case definitions ([Annex 5](#)). Anonymized copies of the medical records including laboratory results and technical examinations may be requested by the experts. If the two experts cannot reach an agreement, then the different clinical opinions of the experts will be listed. This final classification (strictly following the case definitions) will be used for the statistical analyses.

CONFIDENTIAL115055 (EPI-MALARIA-002 VS AME)
Protocol Amendment 7 Final

Children diagnosed with an AESI, will be followed up after hospital discharge up to study conclusion (i.e. study end or child reaches 5 years of age, whichever occurs first) in order to evaluate any sequelae. This will be done by a check-up at the hospital 1 month, 6 months and 1 year after hospital discharge.

9.2.7.4.3. *Children suspected of having a serious adverse event (SAE)*

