	
Exclusion criteria for all levels of diagnostic certitude
 
 Authentication of an acute infection or of a differential diagnosis is compatible with the clinical picture Relapse of the illness at any moment after a minimum period of three months of clinical improvement after the nadir of clinical symptoms. MRI images or histopathology in the clinical diagnosis is compatible with the case definition with the diagnosis of ADEM. 
In Summary
 
ADEM can be confirmed if:
 
 The clinical diagnosis is compatible with the case definition. All differentials diagnoses have been excluded The CSF exam supports the diagnosis of ADEM. 
NB: Plan for diagnostic confirmation by a neurologist (and MRI if possible). Generally the illness completely resolves in a few months. The diagnosis must be confirmed by a clinical examination performed 3 months after the nadir of the clinical symptoms.
	
ENCEPHALITIS	
LEVEL 1
 
 Demonstration of acute inflammation of the central nervous system parenchyma (+/- the meninges) on histopathology 
LEVEL 2
 
 Signs of encephalopathy (depressed level of consciousness, somnolence, acute personality change for more than 24 hours) 
AND
 
One or more of the following signs:
 
 Absent or diminished reflexes to external stimuli (such as a loud noise or painful stimuli) Absent or markedly diminished eye contact Inadequate or absent response to an external stimuli Seizures with loss of consciousness 
OR

CONFIDENTIAL115055 (EPI-MALARIA-002 VS AME)
Protocol Amendment 7 Final

Body system/ AESI	Diagnosis/Level of Diagnostic Certainty	References

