HYPOTONIC HYPORESPONSIVE EPISODE (HHE)	LEVEL 1 
 Hypotonia (muscular weakness) AND 
 Reduction or absence of response to sensory or verbal stimuli AND 
 Pallor or cyanosis LEVEL 2 
 Indeterminate muscle tone AND 
 Reduction or absence of response to sensory or verbal stimuli AND 
 Pallor or cyanosis OR 
 Hypotonia (muscular weakness) AND 
 Reduction or absence of response to sensory or verbal stimuli OR 
 Indeterminate skin color LEVEL 3 
 Normal muscle tone AND 
 Reduction or absence of response to sensory or verbal stimuli AND 
 Pallor or cyanosis OR 
 Hypotonia (muscular weakness) AND 
 Indeterminate response to sensory or verbal stimuli AND 
 Palor or cyanosis. 	Bonhoeffer J, et al. Brighton Collaboration HHE Working Group. Hypotonic- Hyporesponsive Episode (HHE) as an adverse event following immunization: case definition and guidelines for data collection, analysis, and presentation. Vaccine. 2004; 22(5-6): 563–568.

CONFIDENTIAL115055 (EPI-MALARIA-002 VS AME)
Protocol Amendment 7 Final

Body system/ AESI	Diagnosis/Level of Diagnostic Certainty	References
Hepato-Gastrointestinal and Renal System		

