	
Arthritis of acute onset defined as joint swelling or joint pain with limitation on motion.
 
Arthralgia of acute onset defined as joint pain without joint swelling or limitation on motion.
 
 Renal involvement 
Proteinuria >0.3 g/24 h or >30 mmol/mg of urine albumin/creatinine ratio on a spot morning sample. Haematuria or red blood cell casts: >5 red blood cells/high power field or red blood cells casts in the urinary sediment or $\geq 2+$ on dipstick.
 
MINOR CRITERIA
 
 Other diagnoses unlikely (exclude meningitis) 
II) Diagnostic certainty levels
 
LEVEL 1
 
 Purpura or petechiae (mandatory) with lower limb predominance 
AND ≥ 1 following criteria
 
 Abdominal pain Histopathology Arthritis or arthralgias Renal involvement 
AND
 
 Absence of thrombocytopenia 
LEVEL 2
 
 Purpura or petechiae (mandatory) with lower limb predominance 
AND
 
 Absence of thrombocytopenia. 	
JUVENILE CHRONIC ARTHRITIS	
Juvenile Chronic Arthritis is defined by an evolution of symptoms of at least three months. The clinical examination often reveals a child with growth retardation. The different clinical forms are the following:
 
1) Pauciarticular form (the most common form between 1 and 3 years of age). Clinically this presents with:
 
 Involvement of four or less joints Symmetric involvement of the small joints Tenosynovitis of the flexor tendons and erosive nodules (frequent) Rheumatoid factor seronegativity 	
Medical websites resources: e.g. http://www.arthritis.co.za/jra.htm; http://emedicine.medscap.com/article/1007276-overview; http://www.med.univ-rennes1.fr/etud/pediatrie/arthrite_cique.htm

CONFIDENTIAL

115055 (EPI-MALARIA-002 VS AME)
Protocol Amendment 7 Final

Body system/ AESI	Diagnosis/Level of Diagnostic Certainty	References

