DIABETES MELLITUS TYPE 1	
 Serum fasting glucose ≥ 7 mmol/L (> 126 mg/dL) 
OR
 
 Postprandial serum glucose ≥ 11.1 mmol/L (≥ 200 mg/dL) 2 hours after ingesting 1.75 g/kg (max.75g) of glucose (oral glucose tolerance test) 
OR
 
 A1C Hemoglobin $\geq 6.5\%$ AND Hyperglycemia 
AND
 
 No other cause of hyperglycemia 
In Summary The diagnosis of type 1 diabetes mellitus can be confirmed when a confirmed hyperglycemia responds to the case definition.
	WHO Definition and Diagnosis of diabetes mellitus and intermediate hyperglycaemia, 2006 and http://www.nlm.nih.gov/medlineplus/encyclopedia.htm
THROMBOCYTOPENIA	
LEVEL 1
 
 Platelet concentration $< 150 \times 10^9/\text{mL}$ 
AND
 
 Confirmation par blood smear 
OR
 
 Clinical signs of spontaneous bleeding (i.e. non traumatic)* 
LEVEL 2
 
 Platelet concentration $< 150 \times 10^9/\text{mL}$. 
*Spontaneous bleeding (i.e. non traumatic), includes purpura (i.e. petechiae, purpura sensu stricto, ecchymoses) exudative hemorrhage, hematomas, hematemesis, occult bleeding par rectum, epistaxis, hemoptysis, hematuria, vaginal bleeding, conjunctival bleeding, intracranial bleeding.
 
In Summary The diagnosis of thrombocytopenia can be confirmed if:
 
 It corresponds to the level 1 of diagnostic certainty case definition An etiological investigation was carried out. 	Wise RP, Bonhoeffer J, Beeler J, et al. Brighton Collaboration Thrombocytopenia Working Group. Thrombocytopenia: Case definition and guidelines for collection, analysis, and presentation of immunization safety data. Vaccine 2007;25:5717-5724.
Surveillance indicators		

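### Four printed errors in the Annex 5 case definitions (thrombocytopenia, ADEM, HHE, Henoch-Schonlein purpura) give wrong classifications of co-primary AESI if applied as written; how many cases are affected cannot be computed

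*Protocol*

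**What the plan says.** Occurrence of AESI is a co-primary endpoint (Protocol 9.3.1), and Annex 5 holds the case definitions.

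- **Thrombocytopenia.** Levels 1 and 2 share the criterion "Platelet concentration $< 150 \times 10^9/\text{mL". Level 1 adds smear confirmation or spontaneous bleeding, and the bleeding footnote includes purpura and petechiae. Confirmation requires an aetiological investigation and that "It corresponds to the level 1 of diagnostic certainty case definition".
- **ADEM.** Level 1 needs histopathology, or clinical signs with a positive MRI. Level 2 needs a positive MRI. The exclusions for all levels include "MRI images or histopathology in the clinical diagnosis is compatible with the case definition with the diagnosis of ADEM".
- **HHE.** The second branch of Level 2 is hypotonia AND reduced or absent response OR "Indeterminate skin color".
- **Henoch-Schonlein purpura.** Renal involvement may be shown by 24-hour proteinuria above 0.3 g, by ">30 mmol/mg of urine albumin/creatinine ratio on a spot morning sample", or by haematuria or red cell casts. Levels 1 and 2 both require purpura or petechiae and absence of thrombocytopenia.

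On use of the definitions, Protocol 9.2.7.4.2 says of expert-reviewed AESI: "This final classification (strictly following the case definitions) will be used for the statistical analyses". SAP 6.9.3.1 restricts the final analysis to cases confirmed under the protocol definitions. SAP 6.9.2.1 identifies a confirmed AESI by an available ICD-10 code.

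**The concern.** These are decision rules for a co-primary endpoint, and each one, applied literally, puts children in the wrong class. The platelet cut-off and the HHE connector widen their definitions, and the ADEM exclusion narrows its own. The platelet cut-off also reaches a second AESI, because absence of thrombocytopenia is a condition for Henoch-Schonlein purpura. The two AESI have different risk windows (6 weeks and 6 months, SAP Table 1) and belong to different body-system groups (SAP 6.9.2.1), so a child moved from one to the other changes two rates.

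The results are the baseline for EPI-MAL-003, in which events are to be monitored in the same way (Protocol 7.4). If only one study is corrected, the before-after comparison is distorted. If neither is, the published baseline rests on a definition that cannot be the intended one. Amendment 7 edited two other rows of Annex 5 and left these errors in place.

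**Working it through.** **Platelet cut-off.** The documents give no second platelet threshold, so the internal yardstick is the red cell scale in Protocol 9.2.5.5: "percentage of infected red blood cells $> 10\%$; corresponding to $> 500,000/\mu\text{L".

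- Implied red cell count: 500,000 / 0.10 = 5,000,000 per µL = 5 x 10^9 per mL.
- Printed platelet limit: 150 x 10^9 per mL = 150,000,000 per µL.
- Ratio: 150 / 5 = 30. No real platelet count fails the criterion.
- Read per litre, the limit is 150,000 per µL, which is 1000 times lower and 0.03 of the implied red cell count.

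With the numeric criterion always met, Level 2 needs only a count, and Level 1 depends on smear confirmation or bleeding signs, however its AND and OR are grouped. A child with Henoch-Schonlein purpura has purpura or petechiae by definition. With any platelet count, that child meets Level 1 thrombocytopenia and fails the Henoch-Schonlein condition at both levels.

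**ADEM.** The levels and the exclusion, side by side:

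- Level 1 by histopathology: the finding is compatible with ADEM, so the child is excluded.
- Level 1 or 2 by MRI: the same.
- Level 3, which needs no imaging: survives only without supportive MRI or histopathology.

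The same stray phrase about the clinical diagnosis being compatible with the case definition appears in Guillain-Barré Level 1, inside the electromyography item. This points to a faulty text replacement.

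**HHE Level 2.** Give tone, response and skin colour three states each (the sign present, indeterminate, normal): 3 x 3 x 3 = 27 combinations. The first branch of Level 2 contributes 1.

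- Second branch as (hypotonia AND reduced response) OR indeterminate colour: 9 combinations with indeterminate colour, plus 2 more with hypotonia and reduced response. 9 + 2 + 1 = 12.
- Second branch as hypotonia AND (reduced response OR indeterminate colour): 3 + 3 - 1 = 5. 5 + 1 = 6.
- Joined by AND, as in every other HHE branch: 1 + 1 = 2.

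Under the first parse, indeterminate colour qualifies a child with normal tone and response. One of the 12 (hypotonia, reduced response, pallor or cyanosis) is already Level 1. The combinations are not equally frequent, so these counts show breadth and are not rates.

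**Henoch-Schonlein ratio.** Assume a molar mass of albumin of 65,000 to 70,000 g/mol. Then 30 mmol is 0.030 x 65,000 = 1,950 g to 0.030 x 70,000 = 2,100 g, per mg of creatinine. Even at only 1 mg creatinine a day, that is 1,950 / 0.3 = 6,500 to 2,100 / 0.3 = 7,000 times the paired limit of 0.3 g/24 h, so the route is unreachable. With the unit inverted, 30 mg/mmol is 30 / 113.12 = 0.27 mg/mg (assuming creatinine 113.12 g/mol), which is attainable.

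**Weight of one case.** Protocol Table 6 reproduces: for 6 weeks, 10,000 x (1/12 + 1/12 + 6/52 + 6/52) = 3,974.36 PY, and one event is 25.2 per 100,000 PY (exact Poisson limits 0.6 to 140.2). The same table gives 65.0 for 2 weeks and 8.6 for 6 months. In that scenario, one misclassified child shifts the rate by 25.2 (thrombocytopenia, ADEM), 65.0 (HHE) or 8.6 (Henoch-Schonlein) per 100,000 PY.

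**The case against.** The strongest reply concerns reach. The strict-application sentence governs expert review, and only of AESI still uncertain after review by the sponsor's safety physician. Sites diagnose in routine care with Job Aids, which are not among the documents and may carry correct values. The SAP programs no threshold and takes the expert diagnosis, or the investigator's where there is none. Clinicians may have read past the errors. All of this stands, and it is why no count of affected cases can be given. It does not clear Annex 5: the SAP still defines confirmed cases by the protocol definitions, and counting ICD-10 codes has no step that would catch a wrong threshold.

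A reader might go further in three ways that the documents do not support.

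- *Every admission with a platelet count becomes a thrombocytopenia case in the analysed rate.* Confirmation needs Level 1 and a work-up, and the final incidence uses confirmed cases only. Counts are not assured either: Protocol 9.2.7.3.1 expects "All hospitalised children: haemoglobin concentration or full blood count".
- *The ratio unit causes renal Henoch-Schonlein purpura to be under-counted.* Proteinuria, haematuria and casts remain available, renal involvement is one of four alternative Level 1 criteria, and Level 2 needs no renal finding. At most the unit moves a child from Level 1 to Level 2. SAP Table 5 does not split the final rates by level; only the interim Table 7 does.
- *The ADEM rule was deliberately reversed.* The sentence is ungrammatical. Restoring *consistent* where the stray phrase sits yields *inconsistent with the diagnosis of ADEM*, and the same row plans MRI where possible. It is a garbled exclusion that misleads if followed literally.

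A PDF reading error cannot be fully ruled out for the platelet unit, but mL is printed in both levels.

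**Conclusion.** The four errors are in the current Annex 5 and would misclassify co-primary AESI if applied as written. The platelet cut-off matters most: it is 30 times the implied red cell count, is therefore always met, and carries over into Henoch-Schonlein purpura. As printed, ADEM Levels 1 and 2 exclude themselves. HHE Level 2 admits 12 (or 6) of 27 combinations instead of 2. The Henoch-Schonlein unit is wrong but minor.

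That children have in fact been misclassified is a tempting inference, but the documents do not show which text sites and experts used. The number of affected cases cannot be derived from them. The 30-fold ratio rests on the protocol's own parasitaemia conversion. The factor of 1000 assumes that a per-litre unit was intended, which the cited definition must confirm. The Henoch-Schonlein arithmetic rests on the stated molar masses.

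**What to change.** Issue an Annex 5 erratum that reconciles these items with the cited definitions and the Job Aids:

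- platelet unit: per mL to per L;
- albumin/creatinine unit: mmol/mg to mg/mmol;
- ADEM exclusion: MRI or histopathology not consistent with ADEM;
- HHE Level 2, second branch: OR to AND;
- Guillain-Barré Level 1: remove the stray phrase.

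State in the SAP and the study report which version sites and experts applied, and bring EPI-MAL-003 to the same text. Before database lock, re-check recorded suspected and confirmed cases of thrombocytopenia, Henoch-Schonlein purpura, ADEM and HHE against the corrected definitions.

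The cost is an erratum and a modest amount of case review, with no new data collection. The re-check can cover only cases with recorded test results: diagnostic tests are specified as recorded for suspected AESI (Protocol 9.2.7.2.13), whereas the measurement specified for all admissions is haemoglobin, if available (9.2.7.2.11).
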